### 3.2 Hypoxia

Hypoxia is a characteristic feature of malignant tumors that has been well established (16-22). Unlike healthy tissues, tumors often grow at a rate that outgrows their blood supply resulting in the emergence of regions of hypoxia. Immunohistochemical studies have shown nests of hypoxic cells of up to several hundred micrometers in diameter, located at poorly perfused locations within the tumor (23-25). Hypoxia can create selective pressures that render the tumor more aggressive and radioresistant, and has been shown to exhibit an increased likelihood of locoregional recurrence, propensity for metastasis, and poor overall outcome. With invasive measurements, a hypoxia fraction HF2.5 (percentage of measurements <2.5 mmHg) was shown to be the most predictive factor for survival in head & neck cancer (HNC), with a threshold HF2.5 of 20% [17]. In NSCLC, 62% of patients exhibited a HF2.5 < 20% (26).

Locoregional control in non-surgically treated NSCLC patients continues to be a major challenge. Locally-advanced NSCLC patients currently experience freedom from local progression at 3 years (FFLP, defined as intrathoracic tumor progression by World Health Organization criteria) of only 38% and locoregional control (LRC, a stricter definition that requires at least a partial response prior to progression) of 14%, with a 5-year overall survival of approximately 20%, as it was recently demonstrated in a comprehensive review of seven RTOG trials (27). This may at least in part be due to the often large tumor size and significant hypoxia levels in these tumors. PET is a noninvasive imaging modality with the potential to identify tumor hypoxia at both global and local levels through the use of hypoxia targeting molecules. If these hypoxic regions are identified, this will lay the foundation for future studies targeting these hypoxic sub-regions and/or altering treatment regimen, with the ultimate goal to improve the treatment outcome of patients with NSCLC. We and others have previously shown that dose escalation can be successfully given to patients with stage III NSCLC to a maximum tolerated dose (MTD) of 84 Gy (28). This resulted in a promising 2-year local control rate of 52%. RTOG 0117, a phase I/II dose escalation study in patients treated with concurrent chemoradiation, found the MTD to be 74 Gy (29). A pooled analysis of seven RTOG studies of chemoradiation for locally advanced NSCLC found that a 1-Gy increase in biologically effective dose resulted in an approximately 4% relative improvement in survival and a 3% relative improvement in locoregional control (30). Currently, the standard dose for concurrent chemoradiation therapy is 60 Gy. While a recent phase III study (RTOG 0617) appeared to be unsuccessful when escalating the dose to the entire tumor volume to 74 Gy (31), it remains unknown whether escalating the dose to radioresistant tumor subvolumes would not result in better tumor control. Therefore, identifying such subvolumes may provide the basis to a more intelligent dose escalation approach in order to improve the dismal outcomes in stage III NSCLC.

### 3.3 F-FMISO PET Scan and Tumor Hypoxia

Positron emission tomography with F-Fluoromisonidazole (F-FMISO PET) is a non-invasive imaging technique that was shown to be clinically feasible for detecting tumor hypoxia in NSCLC (32, 33). Patients will be given the option to participate in a research study that aims to investigate the prevalence of hypoxia (as determined by F-FMISO PET) in this patient population, and to assess the reproducibility and prognostic value of F-FMISO dynamic PET (dynPET) images in NSCLC patients prior to standard treatment for their lung cancer. Tumor hypoxia is an independent predictor of poor

prognosis in several types of cancer, including NSCLC. Hypoxia imaging may be of particular interest in NSCLC, because it is relatively common in lung cancer, and because the outcome for hypoxic tumors may potentially be improved with more aggressive chemotherapy or radiotherapy, or hypoxia-directed treatments such as the administration of hypoxia activated prodrugs (34, 35) or carbogen breathing (95% oxygen, 5% carbon dioxide) (36). F-FMISO PET has been shown to correlate with hypoxia and treatment outcome in NSCLC (32, 37). Previous study used either qualitative analysis of the dynamic FMISO time activity curves (38) or quantitative analysis of late static FMISO images (37) to identify hypoxia.

The optimal method to quantitate hypoxia using F-FMISO is to perform compartmental analysis of the dynPET images (39-41). This is a method which uses kinetic information from dynamic scans to assess the rate of uptake and entrapment within the hypoxic tumor tissue. However, compartmental analysis is not meaningful on standard clinical PET images of the lung because of respiratory motion during the PET acquisition. Our group at MSKCC has developed a technique for Breath-Hold (BH) PET/CT imaging. During BH PET/CT, patients are asked to hold the breath for as long as possible, and data are acquired only during the time of the BH, using an in-house respiratory tracking device to monitor patient breathing motion (42). PET emission data will be acquired only while the patient is holding the breath as monitored by an external camera and chest sensor. This process will be repeated until a total of 3 min of BH PET data (equivalent to clinical setup) are acquired. We now propose a novel technique to acquire motion-free F-FMISO dynPET images of lung (one 15 cm field of view) to make accurate compartment analysis, and thus quantification of tissue hypoxia, possible. We shall acquire clinical F-FMISO dynPET images in Free-Breathing (FB) with the list mode (LM) option. During the dynamic PET study, the patient's breathing signal will be recorded simultaneously using an in-house developed tracking software assisted by a video camera. The camera is used to monitor the motion of fiducial markers positioned on the patient's abdomen. The patient's breathing signal will be correlated to the PET data on an event-by-event basis and then only those corresponding to end-expiration will be selected for the final PET images, thus resulting in motion-free images. Incorporating all the PET events from the same dynamic PET study results in the FB dynamic PET data set.

In PET/CT, CT images are used to correct for attenuation in the PET images. Spatial matching between PET and CT images is therefore crucial. Therefore, CT images at breathing phases matching those of the PET images will be acquired. PET data will be corrected for attenuation using the phase-matched CT images.

The value of F-FMISO-PET as an early response marker during radiation therapy is still unknown. In a study in 20 patients with head and neck cancer who underwent baseline and mid-treatment FMISO imaging, 90% of patients showed complete resolution of F-FMISO uptake in the mid-treatment scan, suggesting tumor re-oxygenation (43). In the current study, we will assess the predictive value of F-FMISO at 2 weeks +/4 days post-initiation of therapy (~ at a dose of 20Gy). This will allow identification of persistent radioresistant tumor sub-volumes. These data may provide the basis for future response adaptive radiation therapy strategies. For instance, patients with persistent hypoxia, if prognostic of poor outcome, may in a future studies be selected for a site directed additional radiation boost.

In this protocol, both F-FMISO and mid-treatment F-FDG imaging shall be used for exploratory research purposes only; the image findings and results will not be used to change patient management. MSKCC holds an IND for the use of F-FMISO under IRB protocol #04-070 (P.I. [name]).

This protocol shall use F-FMISO under cross-file with IND 115764, since the radiolabeling chemistry and dosage shall be identical to protocol IRB #04-070.

### **3.4 Simultaneous imaging of tumor hypoxia and tumor metabolism**

Imaging hypoxia and metabolism simultaneously may provide a new understanding of the role of the tumor microenvironment; in particular the interplay between hypoxia (defined by FMISO) and tumor cell metabolism (defined by FDG).

F-FMISO and FDG have been shown to be important prognostic and predictive biomarkers in patients undergoing CRT [59, 60]. Identifying simultaneously hypoxic and metabolically active sub-regions within the tumor is a more coherent measurement of the tumor microenvironments than co-registering images acquired in different imaging sessions where temporal changes in the biology and inaccuracies in the image registration curtail the integrity of the data. Previous studies have demonstrated both the feasibility and potential for simultaneous assessment of two physiological processes (mainly in brain) by exploiting temporal [61] kinetic, or daughter outputs (positron vs positron+cascade  $\gamma$ ) (44) differences between radiotracers.

In this protocol, we are going to apply a new method to obtain the information from two F-18 based PET radiotracers (F-FMISO and FDG) in a single PET/CT acquisition. We have developed a preliminary means of decoupling the individual signals with the ultimate goal to use the combined hypoxia/metabolic rate map to guide and adapt CRT, and monitor response in a larger cohort of patients with NSCLC and other malignancies. In preliminary studies, we have successfully established methodology and validated that in both mathematical simulations and animal models, for achieving this objective, and propose to apply this methodology to patients receiving sequential F-FMISO and FDG dynamic PET exams in this study. We propose to conduct compartmental analysis from a single dynamic FMISO and FDG PET acquisition in which FMISO is injected concurrently with the start of the dynamic PET acquisition, followed by an injection of FDG about 45 min +/- 15 min later. We *hypothesize* that simultaneous FMISO and FDG PET imaging will result in prognostic and predictive values that are superior to those achieved when imaging is performed separately for each radiotracer (i.e. in 2 scanning sessions, days apart). We believe this enhancement will be due to (1) exact co-localization of the 2 markers (no co-registration necessary), and (2) absence of inter-scan transient biologic changes. We believe this method will lay the foundation for future studies using dual PET radiotracers in patients with NSCLC and other malignancies, and may have potential implications for dose painting strategies in radiotherapy, adaptive CRT, and assessing response to treatment. If clinically feasible, comparison of the prognostic and predictive values of combined F-FMISO/FDG with those of each of the two radiotracers (when imaged separately) shall be the subject of a future investigation in a larger cohort of lung patients.

### **3.5 Respiratory Motion in PET/CT imaging of the thorax**

Patient's respiratory motion during PET/CT imaging results in artifacts in the PET/CT images due to internal organ motion. In CT images, breathing-induced artifacts are mainly due to the dynamic interaction between transaxial image acquisition and the asynchronous motion of tumor and normal tissue (45). Commonly observed artifacts include distortion of the dome of the liver at the lung-diaphragm interface, splitting of a tumor into multiple distinct parts, out-of-order shuffling of the transaxial slices, and creation of discontinuities in the diaphragm/lung interface (45). In PET, due to

the long acquisition time per bed position (3 to 7 min), PET images are then time-averaged over many breathing cycles (average breathing period is 5 seconds). This results in the blurring of the target volume (42, 46, 47), and reduces the apparent radiotracer uptake (46, 48).

In hybrid PET/CT, respiratory motion can result in hybrid motion artifacts, primarily due to the temporal mis-match between PET images and the corresponding CT-based attenuation map. A common artifact due to the tempo-spatial mis-match between PET and CT is the mis-localization of lesions at the border of two organs (42, 49). The tempo-spatial mismatch between PET and CT images can also result in an increased uncertainty in the apparent tumor SUV due to the use of a non-spatially matching CT image set to correct for attenuation in the PET images. Erdi and co-workers showed dependence of the measured tumor SUV on the breathing phase at which CT images were acquired at.

### **3.6 Correction for Respiratory Motion Artifacts: Deep-Inspiration-Breath-Hold (DIBH) PET/CT**

We have recently developed a novel technique to correct for breathing artifacts in PET/CT images, the Deep-Inspiration-Breath-Hold (DIBH) acquisition(42). We believe DIBH is the most pragmatic and robust approach to eliminate misregistration of PET and CT data. In this approach, the patient is instructed to hold the breath during CT acquisition. The amplitude at which the hold (HA) period occurs is identified using a respiratory tracking system. During PET acquisition, the patient is then instructed to hold the breath at the same (HA), over subsequent periods. PET data will be acquired only while the patient is holding the breath as monitored by an external camera and chest sensor. This will be repeated till a total of 3min of BH PET data are acquired. Finally, PET data corresponding to the hold periods are summed into one data set, and then reconstructed using the corresponding breath-hold CT image set. With DIBH PET/CT (as compared to nonrespiratory motion-corrected PET/CT) we observed as much as an 83% increase in lesion SUV, and as much as 50% improvement in spatial matching between PET and CT(42). DIBH PET/CT had the advantage of reducing misregistration, as both the CT and the PET components were acquired in the same respiratory phase. This was particularly useful for distinguishing between pulmonary and extrapulmonary lesions in the chest wall or mediastinum. Additionally, a small nodule that was not seen on clinical PET/CT showed mild F-FDG uptake on BH PET/CT; this was an additional site of metastasis in a patient with lymphangitic spread. DIBH-PET also results in an improved signal-to-noise ratio, which can yield increasing lesion detectability. In CT, DIBH imaging also resulted in detection of 2.2 additional nodules on average per patient, especially when those nodules were smaller than 0.5 cm(50). DIBH CT also allowed more precise localization and characterization of pulmonary lesions than non-DIBH CT(42, 50).

## **4.0 OVERVIEW OF STUDY DESIGN/INTERVENTION**

### **4.1 Design**

This is a single-institution exploratory study evaluating the prognostic and predictive significance and reproducibility of tumor hypoxia as imaged by F-FMISO PET, in NSCLC patients before receiving any treatments for their disease. In a sub-group of these patients, we will assess the predictive value of F-FDG PET/CT as well. Moreover, in a sub-group of five patients, we will assess the feasibility of simultaneous F-FMISO/F-FDG acquisitions. Patients will be identified in thoracic oncology, radiation oncology, or radiology departments at the time of their planned diagnostic imaging studies.

We will also evaluate the pharmacokinetic properties of F-FMISO during the imaging studies. Moreover, we will evaluate the significance of breath hold (BH) imaging over standard techniques in both F-FDG PET/CT and F-FMISO PET/CT image sets in patients from Group 1, as outlined in Sections 9.1 and 9.2. Patients will be identified and consented prior to their baseline F-FDG-PET/CT. A total of 25 patients will be accrued for this study over a 3 year period; 10 patients who are receiving RT or concurrent chemo RT and 16 patients who are receiving neoadjuvant chemotherapy. The group of 10 patients receiving RT or concurrent chemo-RT will receive an additional repeat F-FDG PET/CT scan at mid-treatment.

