### Schema:

There are two groups currently active in this protocol. Group 1 includes a mid-treatment FMISO PET scan and FDG PET scan. Group 2 includes a sequential injection of F-FMISO and F-FDG. Both groups will have completed a routine pre-treatment FB and breath-hold F-FDG PET/CT and pre-treatment F-FMISO PET Scan.

- Group 1: Perform a routine pre-treatment free-breathing (FB) and breath-hold (for only one PET Field of View, i.e. an additional ~10 min of PET/CT imaging) F-FDG PET/CT. If the patient is planned to receive radiotherapy, the FB PET/CT scan will be used for RT planning.
- Group 2: Perform a routine pre-treatment free-breathing (FB) F-FDG PET/CT. If the patient is planned to receive radiotherapy, the FB PET/CT scan will be used to RT planning.
- Both groups will perform a pre-treatment dynamic F-FMISO PET scan (F-FMISO1). This scan will occur at least one day after the baseline F-FDG PET/CT scan, but prior to initiation of therapy. A baseline F-FDG PET/CT scan may be acceptable provided it is not earlier than one month prior to the F-FMISO study and will assist to define the field of view of the dynamic F-FMISO PET scan. If a CT is available to allow definition of the tumor region, then the F-FMISO may be performed before the FDG PET scan. Dynamic F-FMISO PET images will be corrected for breathing-induced artifacts allowing kinetic analysis to be performed for both the motion-corrected and the free-breathing dynamic PET image sets. The degree of hypoxia within the tumor volume will be estimated by the magnitude of the F-FMISO irreversible trapping rate constant.
- **Group 1 : F-FMISO2/FDG mid-treatment PET/CT:** Perform a mid-treatment dynamic F-FMISO (FMISO2) PET/CT (following the same protocol as for the baseline FMISO) scan in a group of twenty five patients, undergoing RT or concurrent chemo-RT. This scan will occur two weeks +/- 4 days after the start of radiotherapy or the radiation portion of combined chemo-radiation (Diagram 1).

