- Perform a mid-treatment F-FDG PET/CT scan in a group of twenty five patients, undergoing RT or concurrent chemo-RT. This scan will occur two to three weeks +/- 4 days after start of treatment of radiotherapy or the radiation portion of combined chemo-radiation. F-FDG PET/CT scans will be performed in both Free-Breathing (FB) and Breath-Hold (BH) modes. The predictive value of F-FDG, based on the change in lesion SUVpeak between baseline and the 3-week mid-treatment

scan and following the PERCIST criteria, will be assessed using both the FB, and the BH, image sets independently. Results deduced from the FB and BH data sets will be compared and correlated with outcome.

- **Group 2: Combined  $^{18}\text{F}$ -FMISO/ $^{18}\text{F}$ -FDG baseline PET/CT:** In a group of 5 patients, two PET radiotracers  $^{18}\text{F}$ -FMISO and  $^{18}\text{F}$ -FDG will be injected sequentially into the patient. Since all PET radiotracers emit the same 511 keV coincidence photons, it is not possible to discriminate events from these different radiotracers. However, by conducting a dynamic PET/CT scan with staggered  $^{18}\text{F}$ -FMISO and  $^{18}\text{F}$ -FDG injections (45min +/- 15min apart), the kinetic profiles should provide sufficient information to allow signals from the two radiotracers to be clearly separated. This sequential  $^{18}\text{F}$ -FMISO /  $^{18}\text{F}$ -FDG study will be performed at least one day after the sole FMISO1 radiotracer baseline PET/CT scan, and prior to the initiation of therapy. The  $^{18}\text{F}$ -FMISO and  $^{18}\text{F}$ -FDG individual signals will be deduced from the combined dynamic PET images by means of kinetic modeling, and the corresponding radiotracers entrapments within the tumor will be determined. The accuracy of the  $^{18}\text{F}$ -FMISO signal extraction from the combined one in the staggered  $^{18}\text{F}$ -FMISO/ $^{18}\text{F}$ -FDG dynamic PET/CT study will be assessed by comparison to that deduced from the sole FMISO1 study (Diagram 2).

[figure not shown]

Diagram 1. Combined  $^{18}\text{F}$ -FMISO/ $^{18}\text{F}$ -FDG baseline PET/CT

[figure not shown]

Diagram 2. Group 2: Sequential FDG and FMISO treatment group

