## 2.0 OBJECTIVES AND SCIENTIFIC AIMS

The primary objectives of this study are:

- To correlate the presence and extent of hypoxia, as defined by F-FMISO FB and BH PET/CT at baseline with 3-year progression-free survival (PFS) and overall survival (OS).
- To assess the predictive value of F-FMISO PET/CT in lung cancer patients undergoing radiotherapy or concurrent chemoradiotherapy, as measured by Breath-Hold (BH) and Free-Breathing (FB) PET/CT images, and to determine whether BH PET/CT provides greater predictive capability than Free-Breathing (FB) PET/CT.

The secondary objective of this study is:

- To assess the predictive value of F-FDG PET/CT in a group of twenty five lung cancer patients undergoing radiotherapy or concurrent chemoradiotherapy, as measured by Breath-Hold (BH) and Free-Breathing (FB) PET/CT images, and to determine whether BH PET/CT provides greater predictive capability than Free-Breathing (FB) PET/CT.

- To assess the feasibility of simultaneous F-FDG and F-FMISO PET dynamic acquisitions in a group of 5 patients undergoing radiotherapy or concurrent chemoradiotherapy. If successful, our approach would allow multi-radiotracer PET exams on the same day reducing the need for extra patient visits. For the patients who will undergo the dual FMISO/FDG study, the mid-treatment FMISO will be optional.

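### Section 4.1 accrues 25 patients but lists 10 + 16 = 26, and its 10 RT/chemo-RT patients do not match the twenty five given for the mid-treatment scans (1.0) and the FDG analysis (2.0, 14.0)

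*Combined protocol and SAP*

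**What the plan says.** Section 4.1 (Design) gives the total as "A total of 25 patients will be accrued for this study over a 3 year period" and breaks it down as "10 patients who are receiving RT or concurrent chemo RT and 16 patients who are receiving neoadjuvant chemotherapy". It then assigns the mid-treatment FDG scan: "The group of 10 patients receiving RT or concurrent chemo-RT will receive an additional repeat" FDG PET/CT.

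The Schema in Section 1.0 gives a different count. The second FMISO study is a mid-treatment "scan in a group of twenty five patients, undergoing RT or concurrent chemo-RT". The mid-treatment FDG study is likewise a "scan in a group of twenty five patients, undergoing RT or concurrent chemo-RT. This scan will occur two to three weeks" into treatment. The Schema bases the FDG assessment on a comparison of two time points, "based on the change in lesion SUVpeak between baseline and the 3-week mid-treatment" scan.

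Section 2.0 states the secondary FDG objective, including the BH against FB comparison, "in a group of twenty five lung cancer patients undergoing radiotherapy or concurrent chemoradiotherapy, as measured by Breath-Hold" and free-breathing images. Section 14.0 repeats twenty five RT/chemo-RT patients when it describes the concordance analysis.

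Three other sections bear on the total:
- Section 14.0 opens by enrolling 25 patients across RT, neoadjuvant chemotherapy and chemo-RT, and later pools the two treatment groups for the prognostic analysis.
- Section 13.0 replaces withdrawals so that 25 are evaluable, without giving a split.
- Section 7.0 describes how patients receiving chemotherapy alone will be found.

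**The concern.** Two things do not fit. The smaller is that the parts in Section 4.1 add to one more than the total in the same sentence. The larger is that the number of RT/chemo-RT patients with a mid-treatment scan is 10 in the design section and twenty five in the schema, and the objectives and the statistics section also use twenty five.

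The second conflict has two consequences. It leaves open how many patients support the FDG objective. It also leaves open the treatment mix of the study, because a study of 25 that contains twenty five RT/chemo-RT patients has no chemotherapy-only patients left to pool, although Section 14.0 plans to pool both treatment groups. From the plan as written, a reader cannot say how many patients of each type will be accrued, or how many will have each investigational mid-treatment scan.

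**Working it through.** **1. The counts side by side**

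| Section | What is counted | Count |
|---|---|---|
| 4.1 | Total accrual, all treatments | 25 |
| 4.1 | RT/concurrent chemo-RT + neoadjuvant | 10 + 16 |
| 4.1 | Mid-treatment FDG scan | 10 |
| 1.0 (Schema) | Mid-treatment FMISO scan, RT/chemo-RT | 25 |
| 1.0 (Schema) | Mid-treatment FDG scan, RT/chemo-RT | 25 |
| 2.0 | FDG objective, RT/chemo-RT | 25 |
| 14.0 | FDG concordance analysis, RT/chemo-RT | 25 |
| 14.0 | Total enrolment, all treatments | 25 |
| 13.0 | Evaluable patients | 25 |

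**2. Reproducing the stated total.** 10 + 16 = 26, not 25. The total is not reproduced. It would need 10 + 15 or 9 + 16, or one patient counted in both categories (26 − 1 = 25).

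**3. Trying to fit twenty five RT/chemo-RT patients into the study**
- With the total held at 25: 25 − 25 = 0 patients remain for chemotherapy alone. This contradicts the 16 in Section 4.1, the recruitment route in Section 7.0 and the pooling of two groups in Section 14.0.
- With the 16 neoadjuvant patients kept as a separate group: 25 + 16 = 41. This contradicts the total of 25 in Sections 4.1 and 14.0.
- With one patient counted twice: 26 becomes 25, but the group that Section 4.1 assigns to the mid-treatment FDG scan is still 10.

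**4. What the difference means for the mid-treatment SUVpeak-change analysis.** Section 14.0 takes 38% as free of recurrence at 3 years, so 1 − 0.38 = 0.62 have an event. Applying this to the RT/chemo-RT subset is an assumption, because the plan gives no rate for it. Expected events = n × 0.62:
- n = 25: 25 × 0.62 = 15.5
- n = 10: 10 × 0.62 = 6.2

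If the event fraction were 50% to 75%, the figures would be 12.5 to 18.75 events at n = 25 and 5 to 7.5 at n = 10. The ratio is 25/10 = 2.5 throughout. These are progression events; the plan gives no rate from which to count deaths for the survival outcome.

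**5. What the one-patient error means by itself.** Take the plan's hazard ratio of 3.0, equal groups and the same 62%. Schoenfeld power at two-sided 0.05 is Φ(√d × ln 3 / 2 − 1.96), where d is the number of events.
- 25 patients, d = 15.5: Φ(2.163 − 1.96) = 58%
- 26 patients, d = 16.12: Φ(2.206 − 1.96) = 60%

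At one-sided 0.10 the values are 81% and 82%. The plan states neither level nor sidedness. These figures serve only to show that one patient moves power by 1 to 2 points; whether the plan's stated power is right is a separate question.

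**The case against.** The strongest reply is that the categories overlap. Section 14.0 starts the clock at neoadjuvant therapy where it applies, so some patients may have chemotherapy first and radiation later. This could explain 26 against 25. It does not explain 10 against twenty five, because Section 4.1 itself names the 10 as the group receiving the mid-treatment FDG scan, and Section 7.0 expects some patients to receive chemotherapy alone. Replacement under Section 13.0 does not help either: it gives no split, and Section 4.1 states 25 as the number accrued.

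A second reply is that little hangs on it. The FDG analysis is secondary and labelled exploratory and hypothesis-generating, and the scans do not guide care. This stands and limits the weight of the point.

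Four stronger readings are tempting, but the documents do not support them.
- *That 10 is the true count and twenty five the error.* No section says which governs. The text needing correction could equally be Section 4.1.
- *That the BH against FB comparison loses precision by a known factor.* Scaling by √(25/10) = 1.58 describes the standard error of one log hazard ratio. Section 14.0 plans concordance estimates compared between BH and FB in the same patients, and the documents give nothing from which to compute the precision of that paired difference.
- *That the breath-hold n is unsettled because of Group 2.* The Schema opens with "Both groups will have completed a routine pre-treatment FB and breath-hold" FDG PET/CT, but its own Group 2 item specifies free breathing only, and Sections 4.1, 9.1, 9.2 and 11.1.1 place BH imaging in Group 1. The opening sentence is loose; the rule is clear elsewhere.
- *That the FDG predictor is undefined.* Section 14.0 says only SUV, but the Schema specifies change in SUVpeak. If baseline SUV were meant, more patients could contribute and the limit of 10 would not apply.

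**Conclusion.** The inconsistency is real and is not resolved anywhere in the documents. Section 4.1 adds to 26 against a stated 25. More importantly, its 10 patients with a mid-treatment FDG scan cannot be the twenty five named in Section 1.0, or the twenty five RT/chemo-RT patients on whom Sections 2.0 and 14.0 base the FDG analysis. A total of 25 that includes chemotherapy-only patients cannot contain twenty five RT/chemo-RT patients.

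For the SUVpeak-change analysis the size is 25 patients or at most 10, roughly 15.5 or 6.2 progression events. The patient counts come directly from the text. The event counts rest on carrying the 62% over to this subset, and on the analysis being of change to mid-treatment, as the Schema describes. The finding does not show that any planned test fails or that more patients are needed. It shows that a stated sample size cannot be delivered by the design as described, which should be corrected.

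**What to change.** Reconcile Sections 1.0, 2.0, 4.1, 13.0 and 14.0 to a single accrual table whose parts add to the stated total, without presuming which existing count is right. The table should show:
- RT/chemo-RT patients;
- neoadjuvant patients, with anyone who belongs to both categories counted once;
- the five Group 2 patients, marked as inside the 25 or additional to it.

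Then state the resulting n for the mid-treatment FMISO scan, the mid-treatment FDG scan and the FDG BH against FB analysis, and use the same figure in every section that cites it.

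No added enrolment is requested. The cost is wording. The stated n for the FDG analysis may become smaller.
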